**During a BSI** the following procedure will be done: stool collection for bacterial analysis and sIgA measurement. Extra 2 ml of blood will be collected for flagellin and LPS specific IgG levels. The blood will be obtained as soon as possible when the patient is being investigated for a suspected CA-BSI. In the event that the episode does not meet the criteria for a CA-BSI the samples will not be evaluated.

All bacterial isolates obtained during the study from patients will be saved at their respective institutions (CCHMC and University of Michigan) until the end of the study in the event further work with them is required.

**Plasma glutamine analysis:** Plasma GLN will be performed using quantitative ion exchange chromatography.

**Proinflammatory cytokine evaluation:** Analysis will be performed utilizing Luminex xMAP technology (Austin TX) as previously described.

**Measurement of Flagellin and Lipopolysaccharide- specific Immunoglobulin G level:** This will be done using enzyme-linked immunosorbent assay (ELISA) as previously described.

**Safety evaluation:** The study coordinator will contact the family by phone to assess for the development of any serious adverse events on days 15(±7 days), 45 (±7 days), 75 (±7 days), 105 (±7 days), 135 (±7 days) and 165 (±7 days). There will be a 7 day grace period before and after the desired date of safety evaluation phone calls. The phone interview will assess safety and evaluate for any symptoms suggestive of adverse side effects related to L-GLN. If hospitalized, the safety evaluation will occur with the primary caregiver (bedside nurse or parent).

**Additional safety precautions:** If while enrolled in the study the patient develops multiorgan failure or requires vasopressors, the study drug will not be administered.

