**Study Procedures Table for GLN/Placebo group**

	Screening and Consent	Baseline (Day 0)	Day 15	30 day visit	Day 45	60 day visit	Day 75	90 day visit	Day 105	120 day visit	Day 135	150 day visit	Day 165	180 day visit (final visit)	When clinically indicated
Signed informed consent	X														
Medical History		X		X		X		X		X		X		X	
Physical Examination		X		X		X		X		X		X		X	
Blood collection for glutamine, proinflammatory cytokines (TNF- $\alpha$ , IL-1 $\beta$ , IL-6, IL-8) and Antiflagellin and Anti-LPS IgG (2 ml)		X												X	X (During suspected or confirmed BSI)
Weight, length mid arm and head circumference velocities		X		X		X		X		X		X		X	
Nutritional intake evaluation		X		X		X		X		X		X		X	
stool collection for bacterial and sigA analysis		X		X		X		X		X		X		X	X (During suspected or confirmed BSI)
Instruction on how to measure & administer GLN/placebo		X		X		X		X		X		X			
3-day food record completed by family				X		X		X		X		X		X	
Phone interview			X		X		X		X		X		X		
Aspiration of duodenal fluid (~1 ml) and 1 additional biopsy from the duodenum															X

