## **X. Assessment of Efficacy**

**Hypothesis 1:** Enteral GLN supplementation in infants with SBS after massive bowel resection for NEC will decrease BSI, and thereby decrease systemic proinflammatory cytokine concentrations.

**Specific Aim 1:** To perform a double-blind, randomized, placebo controlled, 6-months pilot study of enteral GLN (0.6g/kg) vs. isocaloric, isonitrogenous alanine (placebo) treatment in PN-dependent SBS children due to NEC to evaluate the efficacy of GLN to decrease: a) BSI (primary endpoint) and b) serial serum concentrations of TNF- $\alpha$ , IL-1 $\beta$ , IL-6 and IL-8 (secondary endpoint). **The primary outcome is the incidence of BSI during the 6 months on GLN supplementation.** BSI is defined as laboratory-confirmed, culture-proven bloodstream infections that meet the Centers for Disease Control and Prevention (CDC) definition. This allows for the distinction between catheter related-BSI and other causes of BSI.

**Secondary outcomes:** 1) Plasma proinflammatory cytokine levels (TNF- $\alpha$ , IL-1 $\beta$ , IL-6, IL-8); 2) readmissions and hospital length of stay; 3) proportion of nutrition delivered enterally versus parenterally; 4) stool sIgA levels; 5) Plasma glutamine.

**Expected results:** We expect that the SBS children on enteral GLN supplementation will have significantly fewer BSI and greater decline in blood cytokine levels during the period of therapy.

**Hypothesis 2:** Enteral GLN supplementation will improve somatic growth parameters in Aim 1 patients.

**Specific Aim 2:** To assess the efficacy of 6 months of therapy with enteral GLN on somatic growth parameters [length velocity (primary endpoint), weight velocity, mid arm circumference and head circumference] in Aim 1 subjects and the impact of BSI on these growth parameters.

**The primary outcome for specific aim #2 is length velocity.** Secondary outcomes are growth parameters of weight mid arm circumference and head circumference velocities. These are clinically relevant growth parameters identified by our preliminary data in which SBS children had growth delay with short lengths and smaller head circumferences than infants without NEC or SBS.

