**Data collection:** During CNC/clinic visits (baseline, days 30, 60, 90, 120, 150 and 180) as described above, each child will have weight, length mid arm circumference and head circumference measured in duplicate. These measurements will be done by a trained member of the study staff at each center. The individual at each site will be trained to perform these

measurements according to standard methods previously described. Institutional scales, length boards and measuring tapes will be used at each center.

**Expected results:** We expect that SBS children on enteral GLN supplementation will have more rapid growth as measured by the parameters above. The group with no BSI or decreased BSI (2 episodes) during the study period is expected to have a greater increase in growth parameters compared to the group with > 2 BSI.

**Hypothesis 3:** The gut luminal microbiome is altered in pediatric SBS versus non-SBS controls, correlates with BSI and is altered by enteral GLN supplementation.

**Specific Aim 3:** To comprehensively assess the gut luminal microbiome (using state-of-the art molecular methods) in Aim 1 SBS patients versus non-SBS, age-matched control subjects (primary endpoint), to correlate major bacterial dynamics present in the lumen with BSI due to specific microbes and to explore whether the gut luminal microbiome is altered by enteral GLN treatment.

**Primary outcome:** Increased *K. pneumonia* and *E. faecalis* in the gut microbiome of SBS infants with BSI.

**Secondary outcome:** Alteration in other commensals in the gut luminal microbiome of SBS infants.

**Subjects:** Infants recruited in specific aim 1 (n=48 – subjects- 36; controls- 12) Healthy age matched infants (n=12) will be recruited from the Gastroenterology and surgery clinics.

**Sample Procurement:** Stool samples (~500 mcg), will be obtained from infants' diapers or ostomy bags. Stool specimens will be collected prospectively during visits at baseline, days 30, 60, 90, 120, 150 and 180. **Stool will also be collected whenever the patient has a BSI.**

The controls (12 healthy infants) will have serial stools collected on 4 occasions, each separated by 60 days (baseline, days 60, 120 and 180).

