- 8) Intestinal microbial groups (e.g., species, genera) will be correlated with the treatment or control arms of the GLN supplementation trial and with bacteria identified during any diagnosed BSI. The frequency of rRNA sequences will be interpreted as the relative abundances of organisms in samples of stool and standardized by gram of stool weight. Bacteria present in specimens will be preliminarily identified by use of the Naïve Bayesian Classifier Tool of the Ribosomal Database Project. The strength of association of individual microbial groups with treatment arms and/or main outcome measures will be measured by comparing the abundances of these groups using the non-parametric Kruskal-Wallis test. Experimental reproducibility and inter- and intra-individual similarities in microbial populations will be assessed by calculating and comparing the sequence-abundance-based Morisita-Horn index. In all statistical analyses 2-sided *p*-values less than 0.05 will be considered statistically significant. Results will be corroborated through the phylogeny-based UniFrac metric, which assesses population-wide differences in microbial lineages between different groups of subjects (SBS vs. control). Stool-associated bacteria collected at BSI incidence will be compared to the species identified on blood culture to determine whether intestinal bacteria are potential sources for BSI. Alternatively, absence of particular species from the stool at the time of BSI diagnosis will indicate that lack of specific bacterial species from the stool predisposes to BSI. Tissue samples collected during endoscopy or surgery and intestinal fluid aspirated during endoscopy will be analyzed in parallel with stool samples in order to assess the use of stool samples as proxies for intestinal samples. Patterns will also be reviewed to assess for relationships to enteral feeding rate.

These methods have been used and demonstrated in 2 published studies by one of the collaborators/co-investigators.

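### Samples taken at a BSI are evaluated only if the episode is a CA-BSI, an undefined term, while the rest of the plan covers every confirmed BSI

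*Combined protocol and SAP*

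**What the plan says.** **Section IX.H, During a BSI.** Two samples are taken. For stool, "the following procedure will be done: stool collection for bacterial analysis and sIgA measurement". For blood, "Extra 2 ml of blood will be collected for flagellin and LPS specific IgG levels". The blood trigger is narrower than the paragraph's opening: "The blood will be obtained as soon as possible when the patient is being investigated for a suspected CA-BSI". The paragraph then ends: "In the event that the episode does not meet the criteria for a CA-BSI the samples will not be evaluated".

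**Study Procedures Table for GLN/Placebo group.** The blood row and the stool row carry the same event-driven trigger, "During suspected or confirmed BSI". Neither row mentions catheter association.

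**Section X, Aim 1.** The primary outcome counts laboratory-confirmed, culture-proven BSI meeting the CDC definition. Of that definition the protocol says: "This allows for the distinction between catheter related-BSI and other causes of BSI".

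**Section X, Aim 3.** "Stool will also be collected whenever the patient has a BSI".

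**Section XIII, Aim 3.** Stool bacteria are to be related to the organisms found in any BSI that is diagnosed, and "Stool-associated bacteria collected at BSI incidence will be compared to the species identified on blood culture". The stated purpose is to judge whether intestinal bacteria are potential sources of BSI.

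**The concern.** The evaluation rule in Section IX.H is narrower than the analysis it feeds. Section X treats catheter-related BSI as one category among BSI, so a confirmed BSI can fall outside it. Such an episode counts in the primary endpoint and belongs to the Aim 3 comparison as Section XIII describes it. Under the literal rule, though, its samples are not assayed. The narrower blood trigger adds to this, because blood may not be drawn at all when the suspected infection is not thought to be catheter-associated.

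At stake is the completeness of the Aim 3 stool-to-blood comparison in a trial that will see few episodes. Selecting episodes by catheter attribution also restricts a question about the source of infection on a feature related to source. And because CA-BSI has no stated criteria, the two sites could apply the rule differently.

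**Working it through.** **1. The passages side by side**

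| Place | Episodes covered | Samples |
|---|---|---|
| IX.H, blood trigger | suspected CA-BSI | blood |
| IX.H, evaluation rule | CA-BSI only | the samples (blood; stool on the natural reading) |
| Procedures table | suspected or confirmed BSI | blood and stool |
| X, Aim 3 | every BSI | stool |
| XIII, Aim 3 | every diagnosed BSI | stool against blood culture |

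The table, Section X and Section XIII agree with each other. The two IX.H sentences are the exceptions.

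**2. Does the primary endpoint depend on these samples?** Section XIII (Sample size) gives at least 85% power for 75% versus 30%, 16 per arm, Fisher's exact test, one-sided 10%. Exact enumeration:

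power = sum over x, y of Bin(x; 16, 0.75) × Bin(y; 16, 0.30) × I[one-sided hypergeometric p ≤ 0.10] = 0.857.

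The stated figure reproduces. The enrolment target also follows: 16 / 0.90 = 17.8, rounded up to 18 per arm. The endpoint comes from clinical blood cultures and not from the extra stool and blood, so these figures do not move under either reading of the rule.

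**3. Expected number of BSI.** Inputs are 16 completers per arm and the planning rates of 75% and 30% with at least one BSI. Assume a Poisson count within each arm, so that mean = -ln(1 - rate):

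- 75% arm: -ln(0.25) = 1.386 per infant; 16 × 1.386 = 22.2
- 30% arm: -ln(0.70) = 0.357 per infant; 16 × 0.357 = 5.7
- Total: 27.9, about 28 episodes in 32 infants

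Counting first episodes only, which needs no Poisson assumption: 16 × 0.75 + 16 × 0.30 = 12 + 4.8 = 16.8.

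**4. Episodes lost under the literal rule.** The documents give no share of confirmed BSI that is not catheter-associated, so every share below is an assumption.

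| Assumed share | All episodes (of 27.9) | First episodes (of 16.8) |
|---|---|---|
| 5% | 1.4 | 0.8 |
| 10% | 2.8 | 1.7 |
| 20% | 5.6 | 3.4 |
| 30% | 8.4 | 5.0 |
| 40% | 11.2 | 6.7 |

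At 10-40% the loss is about 3-11 of 28 episodes, or about 2-7 of 16.8 first episodes.

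**The case against.** The strongest reply is that CA-BSI is loose shorthand for a confirmed BSI, and that the sentence only spares the laboratory samples from suspected episodes that are not confirmed. There is support for this. The Stopping Rules (IX.D) move from BSI to catheter-associated BSI and back within one bullet. Recording of Adverse Events (XII) moves between BSI and CA-BSI in the same way. The IX.H paragraph itself opens on BSI. This reading is possible, but the text does not settle it, because CA-BSI has no criteria and Section X draws the distinction. The sentence needs the same correction if that reading was intended.

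These limits on the concern also stand:

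- **Stool.** The rule follows sentences about blood. Including stool is the natural reading, since both are collected in that paragraph, but it is not certain.
- **Other planned analyses.** Section XIII analyses flagellin and LPS IgG only as change from baseline to day 180, and stool sIgA only at days 30 to 180. The stool-to-blood comparison is the named analysis that is exposed.
- **What remains.** Organism data, saved isolates and the scheduled monthly stools are available whatever the rule says.
- **Size.** Infants must be on TPN at enrolment, or off it for fewer than 7 days, so the non-catheter share could be below 10%.

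A reader might infer four stronger points that the documents do not support:

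- **That the samples are thrown away.** The rule says only that they are not evaluated. The Data Management section allows unused plasma and stool to be stored with consent. It also provides for destruction of specimens at the earliest opportunity consistent with the plan, so later recovery is possible but not assured.
- **That the primary endpoint is damaged.** It does not use these samples.
- **That the rule removes the episodes most likely to come from the gut.** The Background reports enteric organisms in 62% of catheter sepsis in SBS, so catheter episodes are informative about gut origin too.
- **That the rule biases a comparison of arms.** Section XIII does not describe the stool-to-blood comparison as an arm contrast, and any subset defined by having a BSI is already formed after randomization.

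**Conclusion.** The conflict is real and should be resolved. Section IX.H limits evaluation to an undefined category, while the procedures table, Section X and Section XIII cover BSI generally. Read literally, confirmed BSI that are not catheter-associated leave the Aim 3 stool-to-blood comparison. The loss would be about 3-11 of roughly 28 expected episodes, or about 2-7 of 16.8 first episodes.

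Those figures rest on the planning rates, full follow-up of 16 infants per arm, the Poisson assumption for the 28, and an assumed 10-40% share. If recurrent BSI cluster in some infants, the total would exceed 28 for the same rates. Under the benign reading, or if nearly all BSI prove catheter-associated, the loss is close to nil.

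**What to change.** In the During a BSI paragraph of Section IX.H:

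1. Change the blood-draw trigger from suspected CA-BSI to suspected BSI, so that it matches the procedures table. Changing only the last sentence would leave some blood undrawn.
2. Replace the last sentence so that stool and blood are evaluated for every episode meeting the BSI definition used in Sections X and XIII. Name both samples explicitly.
3. Define CA-BSI and record it for each episode as a subgroup flag, so that catheter-associated and other BSI can be described separately.
4. State that samples from episodes not confirmed as BSI stay unevaluated.

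The cost is protocol wording plus assays on a small number of samples, about 3-11 episodes under the assumed shares. Sample size, significance level and power do not change.

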### **Clinical GI endoscopy**

Patients with short bowel syndrome/Intestinal failure may have clinical indications for gastrointestinal endoscopies. These indications include:

- Gastrointestinal bleeding
- Persistent feeding intolerance leading to failure to advance enteral feeds

When the patient is scheduled for a clinically indicated gastrointestinal endoscopy, duodenal fluid (approximately 1 ml) will be aspirated into a sterile container. An additional tissue biopsy will also be obtained.

Patients will not have GI endoscopies only as part of the study procedures.

The samples of duodenal fluid and additional tissue collected will be stored in - 80° C freezer. They will subsequently be sent for bacterial composition evaluation at the University of Colorado using pyrosequencing techniques described below.

The following table summarizes Study Procedures:

**Study Procedures Table for GLN/Placebo group**

	Screening and Consent	Baseline (Day 0)	Day 15	30 day visit	Day 45	60 day visit	Day 75	90 day visit	Day 105	120 day visit	Day 135	150 day visit	Day 165	180 day visit (final visit)	When clinically indicated
Signed informed consent	X														
Medical History		X		X		X		X		X		X		X	
Physical Examination		X		X		X		X		X		X		X	
Blood collection for glutamine, proinflammatory cytokines (TNF- $\alpha$ , IL-1 $\beta$ , IL-6, IL-8) and Antiflagellin and Anti-LPS IgG (2 ml)		X												X	X (During suspected or confirmed BSI)
Weight, length mid arm and head circumference velocities		X		X		X		X		X		X		X	
Nutritional intake evaluation		X		X		X		X		X		X		X	
stool collection for bacterial and sigA analysis		X		X		X		X		X		X		X	X (During suspected or confirmed BSI)
Instruction on how to measure & administer GLN/placebo		X		X		X		X		X		X			
3-day food record completed by family				X		X		X		X		X		X	
Phone interview			X		X		X		X		X		X		
Aspiration of duodenal fluid (~1 ml) and 1 additional biopsy from the duodenum															X

**Study procedures of control group:**

Healthy age-matched infants (n=12; 6 at each site) will have serial stools collected on 4 occasions, each separated by 60 days [baseline, days 60(±15), 120(±15) and 180(±15)]. This is abbreviated compared to the study subjects.

A week prior to the scheduled date of stool collection, families will receive a brief medical questionnaire and stool container. They will be instructed to complete the questionnaire and send in with the stool specimen.

They will be provided with a sterile container with instructions to collect stool and bring in to the clinic for storage and analysis. They will be asked to collect stool on the day of the next anticipated clinic visit, put the stool in a sterile container (which may contain RNAlater) which will be supplied to them by the study team. They will put this in a storage bag, keep cool and bring the sample to the clinic visit.

Parents/Primary caregivers drop off stool specimen to the research team at the study site or will arrange with the team for the specimen to be collected from their homes.

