4. The family will be instructed on how to administer GLN and placebo. During the baseline visit, the initial teaching will be done and they will be provided with the premeasured powder. The dose (0.6g/kg/d (0.3g/kg/dose) of GLN or ALA) will be measured out in the research pharmacy based on the weight of the child at the visit into individual packets. Children hospitalized during the study will receive GLN or ALA from the research pharmacy delivered to the patient's bedside to be administered by nursing staff. At subsequent visits (except visit on day 180), this teaching will be repeated as the dose to be administered will change based on the weight of the child. The family will also be given a weekly drug diary to complete in between visits. They will return the drug diary to the study staff during subsequent visits.
5. During the initial visit, stool will be collected into sterile containers and stored at -80°F until analysis for sIgA and bacterial composition evaluation. It is anticipated that the majority of stool will be collected in clinic during the study visit. If stool is collected in clinic, the stool will be stored immediately in the -80°F freezer without any need for DNA stabilizer.

If stool is not collected during this visit, families will be instructed on how to collect stool for evaluation into a sterile container. They will put this in a storage bag and kept cold until picked up by the home health team or delivered to the research team.

Patients already enrolled will be provided with a sterile container with instructions to collect stool and bring in to the clinic visit for storage and analysis. The family will be asked to collect stool 24-48 hours before their clinic visit and put the stool in a sterile container which will be supplied to them by the study team. They will put this in a storage bag and keep cold. They will bring the sample to the clinic visit. RNAlater may be used with samples when samples are unable to be obtained within 24 hours of the clinic visit.

**Stool sIgA analysis:** sIgA will be determined by ELISA as described.

**During baseline visit and visit on day 180** the following additional procedures will be done: Extra 2 ml of blood will be collected for plasma glutamine, proinflammatory cytokines analysis, flagellin and LPS specific IgG levels.

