It is anticipated that stool samples will be collected during the clinic visit. All stool samples will be scooped into a stool container and stored immediately in a -80°C freezer. For samples collected at home, subjects will be instructed to collect in a container containing RNAlater tissue reagent. This will be stored in a cold at home and when delivered to the study team will be stored in -80°C freezer until processed. RNAlater provides immediate stabilization of DNA, RNA, and protein in samples at room temperature. This preserves the in vivo profile of DNA, RNA, and proteins, allowing reliable downstream analysis. Stabilized samples can be transported at 15–25°C for up to 7 days, or stored at 2–8°C for up to 12 months. For longer storage, stabilized samples can be archived at –80°C.

**Small bowel fluid and tissue procurement:** If the patient is scheduled for a clinically indicated gastrointestinal endoscopic procedure; duodenal fluid (~1 ml) will be aspirated and an additional duodenal biopsies will be collected. Specimens will then be stored at -80°C within 10 minutes of obtaining until processing. They will subsequently be sent for bacterial composition evaluation at the University of Colorado using pyrosequencing techniques described below.

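### Stool collection and preservation rules are inconsistent and can differ between SBS infants and controls, so the Aim 3 SBS-versus-control microbiome comparison may be partly confounded by sample handling

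*Combined protocol and SAP*

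**What the plan says.** **SBS infants (Section IX.H, visit procedures, item 5).** For the initial visit: "It is anticipated that the majority of stool will be collected in clinic during the study visit". For such samples, "the stool will be stored immediately in the -80°F freezer without any need for DNA stabilizer". If no stool is passed, the family collects it at home in a sterile container and keeps it cold. For patients already enrolled: "The family will be asked to collect stool 24-48 hours before their clinic visit and put the stool in a sterile container", again kept cold. Then: "RNAlater may be used with samples when samples are unable to be obtained within 24 hours of the clinic visit".

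**Controls (Section IX.H, control group procedures).** Families receive a container about a week ahead. "They will be asked to collect stool on the day of the next anticipated clinic visit", and they are to "put the stool in a sterile container (which may contain RNAlater) which will be supplied to them by the study team". They keep it cool and bring it in, drop it off or have it picked up.

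**Aim 3 sample procurement (Section X), no group named.** Collection in clinic with immediate freezing at -80°C is anticipated. For home samples, "subjects will be instructed to collect in a container containing RNAlater tissue reagent". This section says that RNAlater stabilises DNA, RNA and protein and preserves the in vivo profile.

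**Analysis and data items.** Section X labels SBS versus control the primary endpoint of Aim 3. It then names a primary outcome, *K. pneumonia* and *E. faecalis* in SBS infants with BSI, that does not involve controls. Section XIII, item 8, uses Kruskal-Wallis tests on abundances and UniFrac for SBS versus control, with no term for handling. Section IX.I (Data Collection) lists demographic and clinical items and nothing on specimen handling.

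**The concern.** Controls are not randomised, so nothing in the design balances how their stool is treated against how SBS stool is treated. If place of collection, stabilizer or time to freezing affects measured composition, and these differ by group, part of an apparent SBS effect could come from handling. The reverse is also possible: handling could mask a true difference. If handling is not recorded for each sample, it cannot be reliably reconstructed later. Sites also cannot follow all the instructions as written, so practice may differ between the two centres.

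**Working it through.** **1. The rules side by side**

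| | SBS (IX.H, item 5) | Controls (IX.H) | Aim 3 text (X) |
|---|---|---|---|
| Place | Mostly clinic (initial-visit text); home for enrolled patients | By the family, then brought in, dropped off or picked up | Clinic anticipated; home allowed |
| Timing of home stool | 24-48 h before visit | Day of visit | Not stated |
| RNAlater, home stool | Optional, if not obtained within 24 h of visit | Optional, no criterion | Instructed |
| Clinic stool | Frozen at once, no stabilizer | Not described | Frozen at once |
| Freezer | -80°F | Not stated | -80°C |

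The firmest conflict is between item 5, where RNAlater is conditional and optional, and Section X, where it is the instruction. The control wording is compatible with either but gives no rule. Item 5 is also awkward on its own terms. It asks families to collect 24-48 hours ahead, yet treats a sample not obtained within 24 hours as the special case. Following Section X strictly would not equalise the groups, because clinic stool would be frozen plain and home stool placed in RNAlater.

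**2. Association between group and home collection**

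The plan gives no figure to reproduce. Inputs:
- Scheduled SBS stools: 36 infants × 7 visits = 252 (stools at BSI are extra).
- Scheduled control stools: 12 × 4 = 48.
- Assumption: all 48 control stools are home-collected.
- Assumption: h of the 252 SBS stools are home-collected.

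With no control stool from clinic, the phi coefficient reduces to

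phi = √[ 48 × (252 − h) / (252 × (48 + h)) ]

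| SBS home share | h | Calculation | phi |
|---|---|---|---|
| 10% | 25.2 | √[48 × 226.8 / (252 × 73.2)] = √0.590 | 0.77 |
| 30% | 75.6 | √[48 × 176.4 / (252 × 123.6)] = √0.272 | 0.52 |
| 6/7 | 216 | √[48 × 36 / (252 × 264)] = √0.026 | 0.16 |

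The last row takes the 24-48 hour instruction to govern all six follow-up visits (36 × 6 = 216). Phi here describes place of collection only. It does not measure bias, and it counts repeated stools from the same infant separately. At the low end a different imbalance appears: SBS stool 24-48 hours old against same-day control stool.

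**3. Illustration of the consequence**

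This simulates the Kruskal-Wallis test at two-sided 0.05, with 36 SBS infants and 12 controls, one sample each, no true difference and 3,000 runs per setting. The RNAlater shares and the handling shift are assumptions; the documents give neither. Entries are false-positive rates.

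| Shift (SD) | Same mix, 50%/50% | SBS 20% / control 50% | 25% / 75% | 10% / 90% | 0% / 100% |
|---|---|---|---|---|---|
| 0 | 4.3% | 5.1% | 4.9% | 4.4% | 4.6% |
| 0.5 | 4.6% | 6.9% | 10.5% | 19.8% | 30.0% |
| 1.0 | 4.6% | 12.4% | 26.4% | 59.2% | 80.9% |
| 1.5 | 4.6% | 19.9% | 46.3% | 88.6% | 98.8% |

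With the same handling mix in both groups, the test stays near its nominal level whatever the shift.

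**The case against.** The strongest reply has four parts.

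- **Overlap.** Both Section IX.H and Section X provide for home-collected SBS stool, and item 5 read literally makes it the instruction for six of seven visits. A reader might infer that handling and group largely coincide. The documents do not establish that: the correlation could be as low as about 0.16. This part stands.
- **Separability.** A reader might infer that handling effects could never be separated from the SBS effect. Because the groups overlap, they could be separated if handling is recorded. The case report form and any specimen log are not in the documents, so all that can be said is that the plan does not describe recording it. This part stands.
- **Preservation.** Section X says that RNAlater preserves the profile, and nothing in the documents says that RNAlater and freezing give different compositions. It follows that no bias is demonstrated. It does not follow that none exists, since no comparison of RNAlater with immediately frozen stool is planned.
- **Reach.** A reader might extend the point to sIgA or to all of Aim 3. Control stool is collected for sIgA, but Section XIII plans no SBS-versus-control sIgA test. The named organism outcome lies within SBS infants, and the two randomised arms share one blinded procedure. This part stands and limits the point to one comparison.

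The -80°F entry looks like a unit slip and adds nothing to the confounding argument.

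**Conclusion.** The inconsistency between the three sets of instructions is a matter of text and holds without assumptions. As written, the plan allows place of collection, stabilizer and time to freezing to be associated with group, and it describes neither recording nor adjustment. The SBS-versus-control microbiome comparison may therefore be partly confounded by handling. The correlation of 0.16 to 0.77 rests on all control stools being home-collected and on an SBS home share between 6/7 and 10%. The false-positive rates are illustrations under assumed shares and shifts. The direction and size of any actual bias cannot be derived from the documents. This is a worthwhile correction to one non-randomised comparison in a pilot; it does not affect the trial's primary BSI analysis.

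**What to change.** 1. Reconcile item 5 of the visit procedures, the control group procedures and the Aim 3 sample procurement text into one rule for both groups: same container, same stabilizer choice and same maximum time to freezing. Settle whether enrolled SBS families are expected to collect at home or in clinic.
2. Correct -80°F to agree with the -80°C given in the endoscopy and Aim 3 sections.
3. Record place of collection, stabilizer (yes/no) and hours to freezing for every stool.
4. In Section XIII, item 8, keep all samples in the main SBS-versus-control analysis. Add a sensitivity analysis stratified by or adjusted for handling, with a like-handled subset as supportive only.

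The subset should not be the main analysis. If 10-30% of SBS stools are home-collected, restricting to home stools would drop 70-90% of them (252 × 0.70 ≈ 176 to 252 × 0.90 ≈ 227).

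The cost is a uniform kit, a few recorded fields, protocol wording and one extra analysis.
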